	The intervention will be undertaken in routine PHC facilities in Tanzania and entails the implementation of the ePOCT+ tool for patient assessment and management, with provision of associated POC tests. Healthcare providers will use ePOCT+ throughout their medical consultations for children aged 0-14 years presenting with an acute medical or surgical problem. The tool will not be used for managing emergency cases. These cases will be identified by the tool in the beginning of the consultation (triage stage) and referred immediately to a higher level health facility. The CDSA of ePOCT+ is based on applicable Tanzanian national and international guidelines for pediatric clinical management (TZ version of IMNCI 2014; WHO Pocket Book of Hospital Care for Children 2013; TZ National Guidelines for the Diagnosis and Treatment of Malaria 2014; TZ Standard Treatment Guidelines and Essential Medicines list for Children and Adolescents 2018; Standard Treatment Guidelines & National Essential Medicines List Tanzania Mainland 2017 (Adults);TZ National Guideline for Neonatal care and Establishment of Neonatal Care Unit 2019; TZ National Guidelines for the Management of Tuberculosis in Children 2016; WHO IMAI guidelines 2009). Before implementation, the medical algorithm will be reviewed by Tanzanian key experts in child health (Pediatric Association of Tanzania; Ministry of Health; Muhimbili National Hospital). Most of the algorithm content was previously validated in Tanzania (see background section). Specifically, the tool will guide clinicians on:
	 i) Decision on immediate referral to hospital versus home-based treatment ii) Medical history (questions to ask caregivers and/or children) iii) Physical exam (signs to look for) iv) POC diagnostic tests (which should be performed in a given clinical context) v) Diagnoses vi) Treatments (including medicines and supportive treatments) vii) Counseling (explanation on final diagnoses, treatments, and follow-up)
	B) The algorithm will be regularly updated according to trends in the collected data. The modifications will be designed by clinical experts based on the clinical and microbiological surveillance data collected during the study. Approved changes will then be integrated into the algorithm using the MedAL-Creator tool that allows physicians without any IT/programming skills to modify the decision tree.

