Analyses will follow CONSORT guidelines (Schulz et al. 2010, Piaggio et al. 2012) and intention-totreat (ITT) principles, that is including all participants as randomized. A flowchart will describe the inclusion and follow-up of participants by study arm. Baseline characteristics will be described by study arm with summary statistics such as median and interquartile range or number and percentage; no formal testing between arms will be performed (Pocock et al. 2002). Outcomes will be described by arm using summary statistics. For the non-inferiority comparison between ePOCT+ and the control arm for clinical cure, a CI approach will be used. A figure illustrating the CIs and the non-inferiority margin will be presented. Primary analyses for the non-inferiority comparison will be performed on both the per protocol and ITT sets (Committee for Proprietary Medicinal P 2001). If ePOCT+ is found to be non-inferior to the control in terms of clinical cure rate, then we will assess for superiority using the ITT set. If non-inferiority is established, we will test for significant differences in the co-primary outcome of antibiotic prescription rate. For this outcome, the percentage of patients receiving antibiotics at day 0 will be assessed using multi-level logistic regression model regression with the cluster included as a random effect. Binary secondary outcomes will be evaluated in the same way. All estimates will be reported with 95% confidence intervals (CI).

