### 4.2 Analysis population definitions

Intention-to-treat population: This population includes all patients enrolled in the study, regardless of whether the health care worker used ePOCT+ (intervention arm), or entered the final treatment data in the eCRF (both arms).

Per-protocol population: This population only includes patients enrolled in the study for whom the clinician confirmed the final treatment (or absence of treatment) / referral status within the ePOCT+ tool (intervention arm) or in the eCRF (control arm).

Complete case set: All enrolled subjects for whom the primary endpoint of day 7 clinical cure data was collected (i.e. excluding lost to follow-up patients).

Complete consultation set: All enrolled subjects (intervention or control) for whom at least information on treatments were collected at day 0.

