## 6.2 Analysis methods

Analyses will follow CONSORT guidelines (Campbell, Piaggio, Elbourne, & Altman, 2012; Piaggio et al., 2012; Schulz, Altman, & Moher, 2010; Zwarenstein et al., 2008). Outcomes will be described by arm using summary statistics. For the non-inferiority comparison between ePOCT+ and the control arm for clinical failure, a CI approach will be used using a random effects logistic regression model using the cluster (health facility) and patient as random effects. A figure illustrating the 95% CIs of the ITT and PP relative risk of clinical failure will be presented with the pre-specified non-inferiority margin of 1.3. Non-inferiority will be achieved if the upper-bound of the RR does not surpass 1.3. If ePOCT+ is found to be

non-inferior to the control in terms of clinical failure using the PP population, then we will assess for superiority using the ITT population. Superiority will be achieved if the relative risk CI of the ITT set does not surpass 1. If clinical failure non-inferiority is established, we will test for significant differences in the co-primary outcome of antibiotic prescription rate. Since the documentation of the final treatment in both arms is part of the per protocol definition, only the PP population can be used. For this outcome, the percentage of patients receiving antibiotics at the initial consultation will also be assessed using a random effects logistic regression model with the cluster (health facility) and patient included as random effects. Binary secondary outcomes and additional analyses will be evaluated in the same way. All estimates will be reported with two-sided 95% confidence intervals (CI), except for the non-inferiority analysis which will be reported with one-sided 95% CI. The study will be deemed a success if clinical failure in the ePOCT+ arm is non-inferior to the control arm, and antibiotic prescription at the initial consultation is 25% less in the ePOCT+ arm compared to the control arm.

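### SAP 6.2 ties the non-inferiority finding to the per-protocol set only and has no rule for a conflict with ITT, although protocol 10.3 makes the analysis primary on both sets

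*SAP*

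**What the plan says.** Protocol 10.3 states: "Primary analyses for the non-inferiority comparison will be performed on both the per protocol and ITT sets". It then moves to superiority, and to the antibiotic outcome, once ePOCT+ is found non-inferior. It does not name a set for that finding.

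SAP 6.2 takes several steps:

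- It displays both sets: "A figure illustrating the 95% CIs of the ITT and PP relative risk of clinical failure will be presented", with the margin of 1.3 marked.
- Its criterion names no set: "Non-inferiority will be achieved if the upper-bound of the RR does not surpass 1.3".
- It goes on to superiority on the ITT population if ePOCT+ is "non-inferior to the control in terms of clinical failure using the PP population". This is the only place where a finding of non-inferiority is linked to a set.
- The antibiotic test opens once non-inferiority is established, and the success definition combines non-inferiority with a 25% lower antibiotic prescription. Neither sentence names a set for clinical failure. The antibiotic outcome itself is analysed in PP only.

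SAP 4.2 defines PP as follows: "This population only includes patients enrolled in the study for whom the clinician confirmed the final treatment (or absence of treatment) / referral status". The confirmation is made in ePOCT+ in the intervention arm and in the eCRF in the control arm. ITT keeps every enrolled child, whatever tool was used and whatever was entered. Protocol 8.1.7 explains how the closing questions are reached: after the whole algorithm in intervention facilities, but straight after registration in control facilities.

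**The concern.** The clinical-failure result controls the rest of the trial. The antibiotic hypothesis is tested only if it is favourable, and it is half of the success definition. If PP is taken as the deciding set, both halves of a success claim could rest on PP, with no randomised all-enrolled comparison contributing.

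PP is not a randomised comparison. Whether a child enters it depends on what the clinician does after the facility has been allocated, and the work needed differs by arm. Protocol 6.1 expects an ePOCT+ consultation to average 15 minutes, and protocol 12.2 foresees that some clinicians may be reluctant to use the tool. Incomplete ePOCT+ records are therefore foreseeable. If the children concerned have a different failure risk from those who stay, the PP risk ratio moves away from the all-enrolled one. If they fail more often, ePOCT+ looks safer than it is.

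The SAP has no rule for the case that matters most, in which PP meets the margin and ITT does not. The choice would then be made with the results in view.

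**Working it through.** **The plan's own figure.** Inputs from SAP 3.3: control failure 3%, margin RR 1.3 (0.9 percentage points), one-sided alpha 0.025, power 80%, 900 children per cluster, ICC 0.002.

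- Per arm before clustering: 2 × 0.03 × 0.97 × (1.960 + 0.842)² / 0.009² = 5,640.
- Design effect: 1 + 899 × 0.002 = 2.798.
- 5,640 × 2.798 = 15,781, or 17.53 clusters. Using t quantiles, or adding one cluster, gives 18.53, so 19 clusters and 17,100 per arm.
- 34,200 × 1.1 = 37,620.

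The stated sample size reproduces and is not at issue here.

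**Precision on the risk-ratio scale.** SE(log RR) = √(2 × (0.97/0.03) × 2.798 / 17,100) = 0.103.

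**Effect of PP exclusions.** Let q be the share of ePOCT+ children excluded from PP, and k their failure risk relative to those who stay. Take a true all-enrolled RR exactly at the margin (3.9% against 3.0%). With no exclusions in the control arm:

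- RR in PP = 1.3 / (1 − q + qk)
- P(declare non-inferiority on PP) = Φ[(ln 1.3 − ln RR in PP) / 0.103 − 1.96]

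Example, q = 10% and k = 2: RR in PP = 1.3/1.1 = 1.182, and Φ(0.0953/0.103 − 1.96) = Φ(−1.03) = 15%.

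The formula was checked against a 20,000-run beta-binomial cluster simulation (19 facilities × 900 per arm, cluster-level t interval, loss to follow-up ignored). The documents give no values for q or k, so every row is an assumption.

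| Excluded from PP | RR in PP | Formula, PP alone | Simulated, PP alone | Simulated, both must pass |
|---|---|---|---|---|
| None | 1.300 | 2.5% | 2.8% | 2.8% |
| 5% of ePOCT+, k = 2 | 1.238 | 6.9% | 7.2% | 2.4% |
| 10% of ePOCT+, k = 2 | 1.182 | 15.0% | 15.2% | 2.4% |
| 20% of ePOCT+, k = 2 | 1.083 | 42.5% | 42.2% | 2.4% |
| 10% of each arm, k = 2 in ePOCT+, k = 1 in control | 1.182 | 15.0% | 15.0% | 2.4% |
| 10% of each arm, at random | 1.300 | 2.5% | 2.5% | 2.1% |
| 10% of each arm, k = 2 in both | 1.300 | 2.5% | 2.5% | 1.8% |
| 10% of ePOCT+, k = 0.5 | 1.368 | 0.7% | 0.6% | 0.6% |

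The fifth row shows that equal exclusion rates do not protect PP if the excluded children differ in risk between arms. With the one-sided 95% interval named in SAP 6.2 (nominal 5%), the 10%, k = 2 row (ePOCT+ only) becomes 24.4% on PP alone and 4.8% if both must pass.

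**Bias in the other direction, in ITT.** Suppose 10% of ePOCT+ children are in fact managed as in routine care, at control risk, and the other 90% have RR 1.3. The ITT risk ratio is then 0.9 × 1.3 + 0.1 × 1 = 1.27. ITT understates the harm among users.

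**Power cost of requiring both.** With true RR 1 and 10% excluded at random in each arm, simulated power on the risk-ratio scale is 69.9% for ITT alone, 68.3% for PP alone and 66.3% for both. These values lie below 80% because the planned calculation reproduces on the risk-difference scale. That is a separate matter.

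**The case against.** The strongest reply is that the SAP does not say that PP alone decides. The criterion, the antibiotic gate and the success definition name no set, and the clause naming PP is formally about moving to superiority. This stands. What the SAP contains is an ambiguity that leans towards PP, not an explicit PP-only rule for the whole trial. The lean is real, because no other sentence says which set yields the finding.

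Second, favouring PP in a non-inferiority trial has a rationale. ITT includes children whose clinician did not use ePOCT+, and this can dilute a true harm. SAP 6.2 shows the same worry when it rejects counting losses to follow-up as failures. This also stands. It is a reason to keep PP in the rule, not to leave ITT out.

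Third, the inflation is conditional. It needs exclusions that differ by arm in rate or risk and are related to outcome, and control clinicians can also leave the eCRF unfinished. Random exclusions leave the error at nominal, and lower-risk exclusions make PP conservative. This is correct, and it limits the claim to a possible bias of unknown direction.

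Fourth, a PP–ITT gap would be visible. SAP 4.1 already reports, by arm, the share of enrolled children with a final treatment entered, a flow diagram is planned, and the ITT interval is displayed. That meets the need for reporting, but it does not supply a decision rule.

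**Conclusion.** The point holds as a mismatch between the documents and a missing rule. The protocol makes the analysis primary on two sets. The SAP links the finding to one of them and is silent on disagreement.

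If PP decides alone and the true RR is 1.3, false non-inferiority is about 7% with 5% of ePOCT+ children excluded at twice the failure risk, and about 15% with 10% excluded. It is about 2.4% if both sets must pass. These figures assume no control exclusions, one-sided alpha 0.025, the plan's 3% failure rate and ICC of 0.002, and no loss to follow-up. In every scenario run with exclusions, requiring both kept the error at or below nominal.

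Two stronger readings are tempting, but the documents do not support them:

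- A reader might infer that the protocol already demands success in both sets. It says that the analyses are performed on both, and does not state that both must meet the margin. A both-must-pass rule is the natural reading, but it would be an added sentence.
- A reader might infer from the synopsis line "The tool will not be used for managing emergency cases" that emergencies leave the intervention PP set. The same paragraph has the tool identify them at triage for immediate referral, and a confirmed referral status can qualify a child for PP. Their exclusion is not shown.

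**What to change.** Add to SAP 6.2, before the results are seen:

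> Non-inferiority of clinical failure is established only if the upper confidence bound of the risk ratio does not exceed 1.3 in both the ITT (complete-case) set and the PP set. If the two sets disagree, non-inferiority is not established, the antibiotic hypothesis is not formally tested and success is not claimed.

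Replace the clause that names PP alone with a reference to this rule, and align the wording of protocol 10.3 with it. No new data or models are needed, since both analyses are planned and completion of the final-treatment entry is already reported by arm.

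The cost is a slightly harder claim: about two percentage points of power against PP alone (66.3% against 68.3%), and 3.6 points against ITT alone (69.9%), with 10% random exclusions in each arm and true RR 1.

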## 3.3 Sample size

The primary analysis will evaluate whether the use of ePOCT+ for case management of sick children in PHC facilities 1) results in similar clinical cure at day 7 (non-inferiority analysis), as compared to routine care and 2) decreased antibiotic prescriptions (superiority analysis) at the initial consultation. The sample size was calculated for testing the non-inferiority of the clinical cure outcome, which will require a much larger sample size due to the rareness of clinical failure. In addition, the testing of differences in antibiotic prescription is conditional on satisfying non-inferiority in the clinical outcome. Assuming a failure rate (not being cured at day 7) of 3% in the control arm (corresponding to a 97% clinical cure rate), based on previous studies, the acceptable non-inferiority margin will be a risk ratio of 1.3. This corresponds to the upper bound of the difference in failure rate not exceeding 0.9% if the control group failure rate is 3%. We utilized a fixed risk ratio rather than an absolute risk difference to protect against potential unexpected event rates (Head et al. 2012).

We assumed a cluster size of 900 patients (average of 150 patients per month x 6 months) and an intraclass correlation coefficient of 0.002 in the clinical outcome based on similar studies. To have 80% power to detect a risk ratio 1.3, for a one-sided hypothesis test at alpha of 0.025, we would require 19 clusters and 17,100 patients per arm (total patients n=37,620 assuming 10% loss to follow-up), rounded to a total of 40 HFs and 40,000 patients. However, due to uncertainty regarding the assumptions of the sample size calculation and to capture a wider more representative range of conditions, we will continue recruitment for Phase 1 for a minimum of 6 months.

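### SAP 6.2 assesses non-inferiority of clinical failure with a one-sided 95% CI (alpha 0.05), although the trial was sized for one-sided alpha 0.025

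*SAP*

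**What the plan says.** Design level. SAP 3.3 states: "for a one-sided hypothesis test at alpha of 0.025, we would require 19 clusters and 17,100 patients per arm". Protocol 10.1.1 gives the same alpha and the same numbers, and the protocol synopsis gives the same one-sided 0.025. SAP 3.4, on the ad hoc power recalculation, updates the control-arm failure rate, the absolute margin that follows from it and the enrolment, and leaves the remaining parameters alone. Alpha is therefore still 0.025 there.

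Analysis level. SAP 6.2 uses a confidence-interval approach with the rule "Non-inferiority will be achieved if the upper-bound of the RR does not surpass 1.3". That sentence names no confidence level. The level appears later in the same section, where two-sided 95% intervals are prescribed for all estimates "except for the non-inferiority analysis which will be reported with one-sided 95% CI". The same section also says: "A figure illustrating the 95% CIs of the ITT and PP relative risk of clinical failure will be presented". It does not say whether those intervals are one- or two-sided.

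Protocol 10.3 prescribes 95% intervals for all estimates and makes no exception for non-inferiority. The SAP revision history records only the sample size recalculation.

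**The concern.** A one-sided 95% bound uses z = 1.645 and corresponds to a one-sided 5% test. One-sided alpha 0.025 needs z = 1.960, which is the upper limit of a two-sided 95% interval. The SAP thus sizes the trial at one level and assigns the other to the analysis. The one analysis it exempts from the two-sided interval is the safety comparison.

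That comparison is a gate. Under SAP 3.3 and 6.2 the antibiotic co-primary is tested only if non-inferiority is met, and non-inferiority is one of the two conditions for calling the study a success. The outcome counts children who have not improved by day 7 and non-referred secondary hospitalisations. Elsewhere in 6.2 the SAP defends its complete-case analysis on the ground that the alternative could produce false non-inferiority. A looser bound works against that aim.

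**Working it through.** **Inputs** (SAP 3.3; Protocol 10.1.1 agrees)

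- Control failure: "Assuming a failure rate (not being cured at day 7) of 3% in the control arm".
- Margin: RR 1.3, which is 0.9 percentage points at 3%.
- Power 80%, cluster size 900, ICC 0.002, equal allocation, 10% loss to follow-up.

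**Reproducing the plan's figure at one-sided 0.025**

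- Patients per arm without clustering: (1.960 + 0.842)² × 2 × 0.03 × 0.97 / 0.009² = 5,640.
- Design effect: 1 + 899 × 0.002 = 2.798.
- Clusters: 5,640 × 2.798 / 900 = 17.53. Adding one for the small number of clusters gives 18.53, rounded up to 19.
- A t-based calculation with 2(k − 1) degrees of freedom also gives 19: power is 0.810 with 19 clusters and 0.787 with 18.
- Totals: 19 × 900 = 17,100 per arm, and 2 × 17,100 × 1.10 = 37,620. Both match the plan.

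**The same method at one-sided 0.05**

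- 4,443 × 2.798 / 900 = 13.81. Adding one gives 14.81, rounded up to 15 clusters.
- Power with 19 clusters would be 0.89.

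**False non-inferiority**

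- At a true RR of exactly 1.3 the nominal probability of passing is the alpha of the bound: 0.05 against 0.025, a ratio of 2.
- A beta-binomial simulation (20,000 runs, 20 clusters of 900 per arm, 3% failure, ICC 0.002) gave 5.0–5.5% against 2.5–2.9%.
- At a true RR of 1.35 with 19 clusters, the normal approximation gives about 2.1% against 0.9%.

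**Which observed results pass**

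The rounded target of 40,000 less 10% leaves 18,000 per arm, or 20 × 900.

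- SE(log RR) = √(2 × (0.97/0.03) × 2.798 / 18,000) = 0.1003.
- One-sided 95% bound: 1.3 / exp(1.645 × 0.1003) = 1.102.
- One-sided 97.5% bound: 1.3 / exp(1.960 × 0.1003) = 1.068.
- With 19 clusters the SE is 0.1029 and the limits are 1.098 and 1.063.

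**Power at a true RR of 1.0, log RR scale, 20 clusters per arm**

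- 0.8345 at alpha 0.05 and 0.7444 at alpha 0.025. The difference, about 9% of trials, is the chance that the two rules disagree when the arms are truly equal. At a true RR of 1.3 it is 5% − 2.5% = 2.5%.

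**The case against.** Four points can be made for the plan as it stands.

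- **The sentence concerns reporting.** The decision rule gives no level, the figure's intervals have no stated sidedness, and Protocol 10.3 has no one-sided exception. This is fair as far as it goes. But the one-sided 95% interval is the only one the SAP expressly assigns to this analysis. If it was not meant for the decision, the decision level is undefined and the same edit is needed.
- **The arithmetic does not prove which alpha was intended.** A log RR calculation at 0.05 gives 18.06 clusters, which also rounds up to 19, whereas at 0.025 it gives 22.92, rounded up to 23. This stands. The case for 0.025 rests on the text, which states it three times, and on the 0.9-point calculation that reproduces 19 at that level.
- **The consequences are bounded.** Overall success also requires 25% less antibiotic prescribing, so false success doubles only in so far as that target is met. Protocol 10.3 analyses both the per-protocol and ITT sets. If both had to pass, the error would be no higher than for either alone, but SAP 6.2 ties the next step to the per-protocol set. The two rules disagree only for observed risk ratios between about 1.07 and 1.10. All of this limits the effect without reconciling the two levels.
- **A one-sided 5% level can be defended in some trials.** It would have to be chosen and justified in advance and used in the sample size. Neither document does so.

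**Conclusion.** The concern holds. The SAP plans at one-sided 0.025 and assigns the non-inferiority analysis an interval that means one-sided 0.05, with no explanation. Taken as written, this doubles nominal false non-inferiority at RR 1.3 from 2.5% to 5% and raises the largest passing observed RR from about 1.07 to about 1.10.

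The doubling is a property of the bounds and does not depend on the planning assumptions. The passing limits do: they assume 3% failure, ICC 0.002 and 20 clusters of 900 per arm analysed. SAP 3.4 reports enrolment below expectation. Other things equal, fewer patients would increase the standard error and lower both limits. The point must be settled because this test controls whether the antibiotic comparison is made at all.

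**What to change.** In SAP 6.2, replace the one-sided 95% exception with a statement that non-inferiority is judged by comparing the upper limit of the two-sided 95% CI for the risk ratio (a one-sided 97.5% bound) with 1.3. Say that the figure shows the same interval. For clarity, add that the follow-on superiority assessment against 1 also uses the two-sided 95% CI. The present wording already implies this.

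If the team did intend one-sided 0.05, it should justify that choice and align the protocol synopsis, Protocol 10.1.1 and SAP 3.3 with it. The stated design alpha points to the first option.

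The edit is one sentence, but it affects power. On the absolute-difference scale that reproduces the plan's figure, 19 clusters per arm still give 0.81 at alpha 0.025. On the log RR scale, closer to the SAP's risk ratio criterion, 20 clusters give about 0.74, against about 0.83 with the looser bound. That loss follows from the alpha the plan already states. The recalculation in SAP 3.4 should name its alpha and its scale so that the 80% threshold refers to the test that will be used.
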